**Abstract**

**Objectives:**

**Primary Objectives**

1. To determine if the preparative regimen of Fludarabine (Flu), Clofarabine (Clo) plus Busulfan (Bu) will produce superior progression free survival compared to Fludarabine and Busulfan alone in a phase III randomized controlled trial in patients with acute myeloid leukemia (AML) and myelodysplastic syndrome (MDS) receiving allogeneic stem cell transplantation.
2. Determine the rate of engraftment, toxicity, relapse rate, graft-vs-host disease (GvHD), progression-free survival (PFS) and overall survival (OS) with each regimen.

**Rationale: (Be as concise as possible)**

In this phase 3 randomized controlled trial, we will determine if the Bu-Flu-Clo regimen improves progression free survival compared to the Flu-IV Bu regimen. In the current study we propose to administer IV Bu at a PK-guided dose that yields an AUC of 6000  $\mu$ Mol-min ( $\pm 5\%$ ) for patients up to age 60 and at a systemic exposure of an AUC of 4,000  $\mu$ Mol-min ( $\pm 5\%$ ) for patients ages 61-70 years or with impaired performance status. The pharmacological parameters will be calculated using a pharmacokinetic model derived from our previous data base on the pharmacokinetics of IV Bu analyzed with the ADAPT II program for clinical pharmacokinetics. Bu will be given in combination with Flu and Clo as outlined below. The drugs are given daily for 4 days as preparation for bone marrow or peripheral blood stem cell transplantation for patients with either AML or MDS. The targeted AUC of 6000  $\mu$ Mol-min (and 4,000  $\mu$ Mol-min, respectively) are based on our cumulative experience with the relevant systemic exposure doses in the recently completed and currently ongoing clinical transplant protocols,

**Busulfan pharmacogenetic studies.** The main cytotoxic actions of busulfan is thought to be through DNA inter-strand cross-link formation and of Clo and Flu through inhibition of DNA damage repair through interference with DNA polymerase, Deoxy-Cytidine kinase and ribonucleotide reductase, respectively, as well as through induction of apoptosis through mitochondrial pathways. To investigate whether these biochemical events, and other events linked to Bu resistance/drug cytotoxicity and development of GvHD can be correlated with treatment outcome, we intend to collect blood from patients and study the *in vitro* alkylating effects of busulfan as well as the DNA damage repair inhibition of Clo and Flu. If possible, we also intend to study cytokine activation/release in conjunction with and following the transplant through weekly blood samples during the first month post transplantation. These samples will be analyzed for both serum cytokine levels and for intracellular cytokine activation. We anticipate to elucidate a pattern of cytokine activation that will herald the onset of both toxic events and those of graft vs host disease after the transplant.

**Eligibility: (List All Criteria)**

**Inclusion:**

- 1) Patients must have one of the following hematologic malignancies: a) Acute myeloid leukemia (AML) any stage and cytogenetic risk-group with the only exception being that patients with AML and favorable cytogenetics (t(8;21, inv 16, or t(15;17) who achieve complete remission with one course of induction chemotherapy are not eligible. Patients with treatment related AML are eligible. b) Myelodysplastic syndromes (MDS) with intermediate or high risk International Prognostic Scoring System score (IPSS scores) or treatment related MDS. Patients with low risk MDS are eligible if they fail to respond to hypomethylating agent therapy such as azacitidine or decitabine.
- 2) Age 3-70 years old. Eligibility for pediatric patients will be determined in conjunction with an MDACC pediatrician.
- 3) Performance score of  $\geq 60$  by Karnofsky or PS 0 to 2 (ECOG) (age  $> 12$  years), or Lansky Play-Performance Scale  $\geq 60$  or greater (age  $< 12$  years).
- 4) Negative Beta HCG test in a woman with child bearing potential, defined as not post-menopausal for 12 months or no previous surgical sterilization. Women of child bearing potential must be willing to use an effective contraceptive measure while on study.
- 5) Adequate major organ system function as demonstrated by: Left ventricular ejection fraction of at least 40%.
- 6) Pulmonary function test (PFT) demonstrating a diffusion capacity of least 50% predicted. For children  $\leq 7$  years of age who are unable to perform PFT, oxygen saturation  $\geq 92\%$  on room air by pulse oximetry.
- 7) Creatinine  $< 1.5$  mg/dL. If question about renal function discuss with study chairman and do 24 hour creatinine clearance (clearance should be  $> 50$  ml/min).
- 8) Bilirubin  $< 2.0 \times$  normal (except Gilbert's Syndrome). SGPT (ALT)  $< 200$ . No evidence of chronic active hepatitis or cirrhosis.
- 9) Histocompatible stem cell donor: Patients must have an HLA matched related or unrelated donor (HLA A, B, C and DR) willing to donate for allogeneic hematopoietic transplantation. High resolution allele level typing is required for donors other than genotypically identical siblings.
- 10) No uncontrolled infection. Protocol PI or designé will be final arbiter if there is uncertainty regarding whether a previous infection is controlled on appropriate (antibiotic) therapy.
- 11) Patient or patient's legal representative, parent(s) or guardian able to sign informed consent.

**Exclusion:**

- 1) Positive for HIV, HBsAg, HCV or other viral hepatitis or cirrhosis from any cause.
- 2) Prior allogeneic or autologous stem cell transplant using a myeloablative busulfan or total body radiation containing conditioning regimen defined as busulfan-based using a total dose of  $\geq 12$  mg/kg given by mouth or  $\geq 10$  mg/kg given IV; or a total-body irradiation ( $> 4$  Gy).
- 3) Active or prior CNS leukemia, unless in complete remission for at least 3 months.
- 4) Previous therapeutic XRT to the liver as part of involved-field radiation.
- 5) History of serious chronic mental disorder or drug-abuse accompanied by documented problems of compliance with therapeutic programs.
- 6) Lack of care-giver for the early (100-day) post-transplant period.

**Are patients  $< 18$  years of age eligible to participate in this study?**

Yes  No

**Studies that include children must meet the criteria for inclusion.**

[http://www.fda.gov/ohrms/dockets/AC/04/briefing/4028B1\\_05\\_NIH-Inclusion%20of%20Children.doc](http://www.fda.gov/ohrms/dockets/AC/04/briefing/4028B1_05_NIH-Inclusion%20of%20Children.doc)

<http://www.hhs.gov/ohrp/policy/populations/children.html>

**Are participants  $> 65$  years of age eligible to participate in this study?**

Yes  No

**Are pregnant women eligible to participate in this study?**

Yes  No

**Will the recruitment population at M. D. Anderson include persons who are incarcerated at time of enrollment (e.g., prisoners) or likely to become incarcerated during the study?**

Yes  No

**Disease Group:**

Blood And Marrow Transplantation, Leukemia

**Treatment Agents/Devices/Interventions:**

ATG, Busulfan, Clofarabine, Fludarabine

**Proposed Treatment/Study Plan:**

Is treatment assignment randomized?  Yes  No

Is this a blinded or double-blinded study?  Yes  No

Allogeneic graft.

Peripheral blood (PB) or bone marrow (BM) progenitor cells may be used in this study.

Preparative Regimen.

Patients will be randomized to received either Flu/Bu or Flu/Clo/Bu and further stratified based on disease status, in complete remission (CR) or not in CR (NCR), at time of protocol entry/start of therapy.

Prior to initiating chemotherapy in this study, all toxicities from prior systemic chemotherapy must be resolved at least to grade 1. Flt3 or TKI inhibitors as well as intra-thecal therapy, nonmyelosuppressive agents, low dose cytarabine, hydroxyurea are permitted if indicated to control active leukemia, but must be stopped at least 5 days prior to administering the PK-test dose of IV Busulfan to avoid pharmacologic interference with IV Bu.

Acetaminophen should not be used between D-10 (starting 24 hours before the test dose of IV Bu) and D0. Other drugs known to interfere with the metabolism of Flu and/or Bu should not to be concomitantly used during the chemotherapy administration up to and including the day of transplantation. day following the stem cell transplant procedure.

Busulfan test dose:

The Busulfan test dose can be administered within 10 days prior to admission as an outpatient or as an inpatient.

Pharmacokinetic-guided (PK-guided) treatment: The Bu "test dose" of 32 mg/m^2 will be based on actual body weight. This Bu dose will be given IV over 45 minutes (for patients up to age 60) and over 60 min (for patients ages 61-70) by controlled-rate infusion pump.

Busulfan adjusted dose determined to achieve a systemic exposure represented by an average daily AUC of 6000 µMol-min ± 5% for the entire 4-day treatment period is administered to all patients up to age 60 who have ECOG performance status 0 or 1 or Karnofsky/Lansky 90-100. The target AUC is 4,000 µMol-min ± 5% for patients ages 61-70 and younger patients with ECOG performance status 2 or Karnofsky 60-80. If pharmacokinetic analysis cannot be completed for any reason, Bu will be given in a dose of 130 mg/m^2 dose (for the target AUC 6000) and 100 mg/m^2 (for target AUC 4000).

Fludarabine/ Clofarabine/ Busulfan

Fludarabine administration:

Flu is administered at a dose of 10 mg/m^2 in 100 ml of NS on each of four (4) consecutive days (days -6 through -3). Intravenous fluids should be administered at a rate of that is ≥ 65 mL/m^2/hour starting the evening before the start of Flu, through twenty-four (24) hours after the last dose of Bu.

#### Clofarabine administration:

Clo will be dosed per actual body weight/actual body surface area. Clo is administered at a dose of 30 mg/m^2 diluted in NS to produce a final concentration of 0.4 mg/mL, and infused on each of four (4) consecutive days (days -6 through -3). The doses of Clo are to follow immediately after Flu administration and prior to Bu on days -6 to -3 respectively. Intravenous fluids should be administered at a rate of that is  $\geq$  65 mL/m^2/hour starting the evening before the start of this chemotherapy, through twenty-four (24) hours after the last dose of Bu.

#### Busulfan administration:

The PK-guided daily high-dose Bu dose(s) will be started immediately upon completion of the daily Clo dose. The Bu doses will be diluted in normal saline or 5% dextrose in water and administered daily by controlled rate infusion pump. Bu is administered at the dose calculated to achieve a systemic exposure dose of 6000  $\mu$ Mol-min in normal saline IV every twenty-four (24) hours for four (4) consecutive days (days -6 to -3), starting immediately after the completion of Clo. The Bu dose on day -6 to -3 will be based on the pharmacokinetic studies to target an AUC of 4,000  $\mu$ Mol-min  $\pm$  5% for patients 61-70 years of age or younger patients with ECOG performance status 2 or Karnofsky 60-80. If pharmacokinetic analysis cannot be completed for any reason, Bu will be given in a dose of 130 mg/m^2 dose.

The PK adjusted dose of Bu=Target AUC x Bu mol. wt (0.2463) x Bu gross the measured clearance normalized to body surface area (L/min) + the dose remaining in the IV line (priming dose).

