##### Busulfan administration:

The PK-guided daily high-dose Bu dose(s) will be started immediately upon completion of the daily Flu dose. It is administered identically to the Fludarabine/clofarabine/busulfan group.

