#### **Statistical Considerations:**

**Treatments and Outcomes.** This is phase III clinical trial of allogeneic stem cell transplantation for AML/MDS patients, having age between 3 and 70 years, who are either in complete remission or not in CR (NCR). All patients will be randomized between two preparative regimens. Both regimens have been studied in recent MDACC trials and found to be adequately safe and effective, warranting this randomized comparison. The first preparative regimen (FluBu) consists of fludarabine (dose = 40 mg/m^2) + intravenous (IV) busulfan using a subgroup-specific PK targeted dose (target dose = 6000 micromolar x minute in patients up to age 60 with ECOG performance status 0 or 1 or 4000 for patients 61-70 years of age or performance status 2). The second preparative regimen (FluCloBu) consists of fludarabine (dose = 10 mg/m^2) + clofarabine (dose = 30 mg/m^2)+ IV busulfan dosed in the same manner. The primary endpoint will be T = progression-free survival (PFS) time, defined as the time from date of transplant to death from any cause or disease progression. Secondary endpoints will include overall survival (OS) time, and the indicator G100 that the patient has grade 3 or 4 acute graft-versus-host disease at any time during the first 100 days post transplant.

**Design and Trial Conduct.** 250 patients will be entered. The two preparative regimens, FB and FCB, will be compared in terms of PFS time using a group sequential design(38) with two-sided O'Brien-Fleming boundaries, with up to two interim tests and one final test, having overall Type I error .05 and power .90

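### The two busulfan fallback rules disagree for AUC 4000 patients: 100 mg/m² in the general treatment plan, 130 mg/m² in the Busulfan administration section

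*Combined protocol and SAP*

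**What the plan says.** The protocol sets two busulfan exposure targets, a daily AUC of 6000 and one of 4000 µMol-min, each ± 5%. Four places assign the lower target to older or less fit patients:

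- Rationale: "for patients ages 61-70 years or with impaired performance status".
- Proposed Treatment/Study Plan, under the test dose: "for patients ages 61-70 and younger patients with ECOG performance status 2 or Karnofsky 60-80".
- Busulfan administration (Flu/Clo/Bu arm): "for patients 61-70 years of age or younger patients with ECOG performance status 2 or Karnofsky 60-80".
- Statistical Considerations: "4000 for patients 61-70 years of age or performance status 2".

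The fallback for a patient without usable PK appears twice. Under the test dose in Proposed Treatment/Study Plan there are two doses, each tied to a target: "130 mg/m 2 dose (for the target AUC 6000) and 100 mg/m 2 (for target AUC 4000"). In Busulfan administration for the Flu/Clo/Bu arm, directly after the sentence that names the AUC 4000 group, there is one: "If pharmacokinetic analysis cannot be completed for any reason, Bu will be given in a dose of 130 mg/m 2 dose". The Flu/Bu arm has no busulfan rule of its own. Its section says: "It is administered identically to the Fludarabine/clofarabine/busulfan group".

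**The concern.** Both statements are current dosing instructions for the same event, and for AUC 4000 patients they give different doses. Neither refers to the other, and nothing in the documents says which governs.

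The shorter statement is hard to read as covering only the AUC 6000 patients, because the sentence just before it is about the AUC 4000 group. The dose formula that follows it cannot help either, since it needs a clearance value from the patient: "The PK adjusted dose of Bu=Target AUC x Bu mol. wt (0.2463) x Bu gross the measured clearance normalized to body surface area". When PK has failed, 130 mg/m² is the only usable rule left in the section that someone preparing the dose would naturally consult.

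At stake is the busulfan dose of patients whom the protocol deliberately assigns to lower exposure. This is a matter of dosing safety and internal consistency. The design choice of two targets is not in question.

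**Working it through.** **Inputs**

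| Item | Value | Source |
|---|---|---|
| Fallback, target 6000 | 130 mg/m² per day | Proposed Treatment/Study Plan |
| Fallback, target 4000 | 100 mg/m² per day | Proposed Treatment/Study Plan |
| Fallback, no target named | 130 mg/m² per day | Busulfan administration, Flu/Clo/Bu arm |
| Treatment days | 4 (days -6 to -3) | Busulfan administration |
| Median AUC at fixed 130 mg/m² in prior studies | 5000 µMol-min | Rationale for Exemption |

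The plan derives neither fallback dose from a calculation, so there is no figure of its own to reproduce. The check is a comparison of the texts and a few ratios.

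**Step 1. Where the rules differ.** For a 6000-target patient both places give 130 mg/m², so there is no conflict. For a 4000-target patient one place gives 100 and the other 130.

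**Step 2. Size of the difference for a 4000-target patient.**

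- Daily: 130 / 100 = 1.30, that is 30% more.
- Course: 4 × 130 = 520 against 4 × 100 = 400 mg/m², a difference of 120 mg/m².

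**Step 3. Separation between the two target groups.**

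| Situation | 4000 group / 6000 group | Reduction |
|---|---|---|
| PK available (target AUC) | 4000 / 6000 = 0.67 | 33% |
| No PK, general treatment plan (dose) | 100 / 130 = 0.77 | 23% |
| No PK, Busulfan administration section (dose) | 130 / 130 = 1.00 | 0% |

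The first row compares exposures and the other two compare doses. Under the shorter rule the reduction disappears for patients without usable PK. Patients with PK are unaffected.

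**Step 4. Which dose fits the lower target.** This step assumes that AUC is proportional to dose and that the prior-study median applies to these patients.

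- At 100 mg/m²: 5000 × 100 / 130 = 3846, which is 3.8% below 4000 and inside the ± 5% window of 3800 to 4200.
- At 130 mg/m²: 5000, which is 5000 / 4000 - 1 = 25% above the target.

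So 100 mg/m² fits the 4000 target and 130 mg/m² does not. This is a plausibility check on a median. Individual AUCs at 130 mg/m² mostly ranged from about 3500 to 7500. Steps 1 to 3 do not depend on it.

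**The case against.** The strongest reply is that the documents already contain the answer. The general text comes before the arm-specific sections, covers both arms and ties each fallback dose to its target. The shorter sentence leaves out the second dose but does not cancel it, and a specific rule normally overrides a general one. Nor can the Busulfan administration section be used alone: it gives the 6000 target without saying who receives it, and it has no test dose or infusion time, so staff need the general text in any case. This stands in part. It shows which dose is intended and makes an error less likely. It does not remove the conflict, because the shorter sentence reads as a complete rule and gives no cue to look elsewhere.

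A second reply is that the event is rare and not shown to be harmful. A misdose needs a 4000-target patient, failed PK and staff who rely on the shorter sentence, all at once. The Rationale for Exemption reports no increase in toxicity across AUCs of roughly 3500 to 7500. It is fair that frequency is unknown and harm not demonstrated. But that section does not give the age or performance status of those patients, so it cannot justify setting aside a lower target meant for older or less fit patients.

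A third reply is that fuller dosing text may exist outside the supplied document, which refers to a treatment scheme not included here. That is possible and cannot be checked. The two statements that are present would still need to agree.

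**Conclusion.** The concern holds. The fallback sentence in the Busulfan administration section is wrong as written for AUC 4000 patients, and it reaches both arms. Followed literally, it gives them 30% more busulfan than the general treatment plan specifies, 120 mg/m² more over the course. The dose figures come straight from the protocol and rest on no assumption. Only the supporting argument that 100 mg/m² matches the 4000 target relies on dose-proportional AUC and the prior-study median.

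The scope is narrow: 4000-target patients without usable PK. How many there will be cannot be derived, because no PK failure rate is given. Since the same instruction applies in both arms, it creates no between-arm bias, and it has no bearing on sample size or type I error. It should still be corrected, because two different doses of a high-dose conditioning drug should not both stand for the patients meant to receive less of it.

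**What to change.** In Busulfan administration for the Flu/Clo/Bu arm, replace the fallback sentence with one that gives both doses: without completed PK, busulfan is dosed at 130 mg/m² per day for patients with target AUC 6000 and at 100 mg/m² per day for patients with target AUC 4000. The section then agrees with Proposed Treatment/Study Plan. The Flu/Bu section inherits the correction and needs no edit.

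The cost is one sentence, with no extra patients or procedures and no change to the analysis.

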#### Fludarabine/ Busulfan

##### Fludarabine administration:

Flu is administered at a dose of 40 mg/m^2 in 100 ml of NS on each of four (4) consecutive days (days -6 through -3). Intravenous fluids should be administered at a rate of that is  $\geq$  65 mL/m^2/hour starting the evening before the start of Flu, through twenty-four (24) hours after the last dose of Bu.

##### Busulfan administration:

The PK-guided daily high-dose Bu dose(s) will be started immediately upon completion of the daily Flu dose. It is administered identically to the Fludarabine/clofarabine/busulfan group.

#### D-3 to D-1 Anti-thymocyte globulin administration:

Patients in both groups who receive a graft from an unrelated donor will receive Thymoglobulin; 0.5 mg/kg on day -3, 1.5 mg/kg on day -2 and 2.0 mg/kg on day -1. On day -3, this will be administered after the chemotherapy is complete (see Treatment Scheme below).

#### Stem Cell infusion

Fresh or cryopreserved bone marrow or peripheral blood progenitor cells will be infused on day 0. The goal is to infuse 5 X 10^6 CD34+ cells/kg if PB or >3.0 X 10^8 marrow mononuclear cells/kg if BM. Premedication for the infusions will be per standard SCTCT department procedures.

#### Prophylaxis and Supportive Care as per standard practice in patients receiving allogeneic transplant and SCTCT Guidelines

##### GvHD with Tacrolimus and Mini Methotrexate with dose adjustment as clinically indicated.

Tacrolimus will be administered at starting dose of 0.015 mg/kg (ideal body weight) as a

24 hour continuous infusion daily adjusted to achieve a therapeutic level of 5-15 ng/ml.

Tacrolimus is changed to oral dosing when tolerated and can be tapered off after day +90

if no GvHD is present. Methotrexate 5 mg/m^2 will be administered intravenously on days 1, 3, 6 and 11 post transplant. Day 11 methotrexate may be held if the patient has symptomatic mucositis.

#### **Study Enrollment:**

The study population for this research will consist of participants from:

Only at MDACC

#### **Estimated Accrual:**

Total Accrual at MDACC: 250  
Estimated monthly accrual at MDACC: 7

#### **Accrual Comments:**

Up to 250 patients will take part in this study. All will be enrolled at M. D. Anderson. We estimate that an average of 7 patients will be enrolled each month, based on our prior experience.

**Is this an NCI-Cancer Therapy Evaluation Protocol (CTEP)?** No

**Is this an NCI-Division of Cancer Prevention Protocol (DCP)?** No

#### **Statistical Considerations:**

**Treatments and Outcomes.** This is phase III clinical trial of allogeneic stem cell transplantation for AML/MDS patients, having age between 3 and 70 years, who are either in complete remission or not in CR (NCR). All patients will be randomized between two preparative regimens. Both regimens have been studied in recent MDACC trials and found to be adequately safe and effective, warranting this randomized comparison. The first preparative regimen (FluBu) consists of fludarabine (dose = 40 mg/m^2) + intravenous (IV) busulfan using a subgroup-specific PK targeted dose (target dose = 6000 micromolar x minute in patients up to age 60 with ECOG performance status 0 or 1 or 4000 for patients 61-70 years of age or performance status 2). The second preparative regimen (FluCloBu) consists of fludarabine (dose = 10 mg/m^2) + clofarabine (dose = 30 mg/m^2)+ IV busulfan dosed in the same manner. The primary endpoint will be T = progression-free survival (PFS) time, defined as the time from date of transplant to death from any cause or disease progression. Secondary endpoints will include overall survival (OS) time, and the indicator G100 that the patient has grade 3 or 4 acute graft-versus-host disease at any time during the first 100 days post transplant.

**Design and Trial Conduct.** 250 patients will be entered. The two preparative regimens, FB and FCB, will be compared in terms of PFS time using a group sequential design(38) with two-sided O'Brien-Fleming boundaries, with up to two interim tests and one final test, having overall Type I error .05 and power .90

to detect an improvement of  $\text{Pr}(T > 12 \text{ months})$  from a null value of .56 to a target value of .71, equivalently, to detect a change in median PFS from 14.35 to 25.29 months. The null value of  $\text{Pr}(T > 12 \text{ months})$  was determined by assuming that  $\text{Pr}(T > 12 \text{ months} | \text{CR}) = .65$  and  $\text{Pr}(T > 12 \text{ months} | \text{NCR}) = .50$ , based on experience with Flu + IV Busulfan, and the assumption that  $\text{Pr}(\text{CR}) = .40$ , giving null  $\text{Pr}(T > 12 \text{ months}) = .40 \times .65 + .60 \times .50 = .56$ . The decision boundaries, in terms of the standardized log rank statistic, are  $+/-.3.7103$ ,  $+/-.2.5114$ ,  $+/-.1.993$  to be applied when, respectively, 52.16, 104.31, and 156.46 events (death or progression) have been observed in both arms combined. The Pocock-Simon method will be used to dynamically balance the randomization on the binary (CR, NCR) indicator, using the Department of Biostatistics Clinical Trial Conduct website.

**Data Analyses.** Kaplan-Meier plots will be used to estimate the unadjusted OS and PFS time distributions. Time-to-event regression analyses will be used to evaluate the ability of treatment arm and patient covariates to predict OS and PFS, with the model underlying model chosen based on preliminary goodness-of-fit analyses of the data. The rate of 100 day severe GvHD will be estimated by tabulations and computation of posterior credible intervals, overall and within the CR and NCR. To account for the treatment and baseline covariates,  $\text{Pr}(\text{GvHD within 100 days})$  will be estimated using logistic regression.

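### Primary PFS is timed from transplant, after all the treatment that differs between arms, and no rule covers randomised patients who are not transplanted

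*Combined protocol and SAP*

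**What the plan says.** Under Statistical Considerations (Treatments and Outcomes), "All patients will be randomized between two preparative regimens". The primary endpoint is PFS, "defined as the time from date of transplant to death from any cause or disease progression". For survival the text says only "Secondary endpoints will include overall survival (OS) time", with no time origin.

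The treatment sections place everything that differs between the arms before that starting point. Fludarabine is 10 mg/m² in the clofarabine arm and 40 mg/m² in the control arm, and clofarabine 30 mg/m² is given in one arm only. All of these are given daily on days -6 to -3. Busulfan is given the same way in both arms, and anti-thymocyte globulin depends on donor type in both. Under Stem Cell infusion, "Fresh or cryopreserved bone marrow or peripheral blood progenitor cells will be infused on day 0".

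Neither Statistical Considerations nor Protocol Monitoring names an analysis population. Neither says what happens to a patient who dies, progresses or has the transplant cancelled between randomisation and day 0, and neither has a replacement rule. The date of randomisation is not fixed. It must fall no later than day -6, when the first differing dose is given.

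**The concern.** Randomisation makes the two groups comparable when they are assigned. The endpoint starts at least six days later, after the assigned drugs have been given, and is defined only for patients who reach transplant. If one regimen causes more deaths or cancelled transplants during conditioning, those patients drop out of the primary comparison and their failures are not charged to that regimen. The error can favour either arm.

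Two further gaps follow. It is unclear whether a progression before day 0 counts when the patient is still transplanted. Because exclusion of untransplanted patients is implied by the definition but not stated, the analysis set could also be settled, or reopened, after the data are seen.

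**Working it through.** **1. The plan's own design.** The inputs from Statistical Considerations are 12-month PFS .56 v .71, boundaries 3.7103, 2.5114 and 1.993 at 52.16, 104.31 and 156.46 events, two-sided alpha .05 and power .90. Under exponential times, HR = ln(.71)/ln(.56) = 0.591. With 1:1 allocation, the three-look crossing probability is 0.0500 under the null. Power is 0.905 with the Schoenfeld approximation and 0.892 with Freedman's, so the stated .90 reproduces.

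**2. Scale.** The documents give no pre-transplant failure rate. The only yardstick they supply is the control hazard, -ln(.56)/12 = 0.0483 per month. Over six days this gives 1 - exp(-0.0483 × 6/30.44) = 0.9%, or about 1 patient of 125 per arm. It is an average over follow-up and not specific to conditioning. All failure rates below are assumptions.

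**3. No true difference after transplant.** The simulation used 125 patients per arm, accrual of 250 at 7 per month, and the control hazard in both arms after transplant. Pre-transplant failures were spread evenly over the six days before day 0. Mean z is the unstratified log-rank at month 46 (6,000 runs). Boundary crossings use three looks at 53, 105 and 157 events (16,000 runs).

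| Failures before day 0 | Shift in mean z against the worse arm, from randomisation | Crossing against the worse arm, from randomisation |
|---|---|---|
| 1% v 2% | 0.10 | 3.5% |
| 2% v 4% | 0.19 | 4.2% |
| 2% v 6% | 0.39 | 6.4% |
| 1% v 7% | 0.57 | 9.5% |

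Timed from transplant, mean z stays within about 0.02 of zero in every row, and crossings stay at 2.5 to 2.7% in each direction. Reversing the rates (4% v 2%) moves the from-randomisation z by 0.19 the other way, and equal rates move it not at all. Smaller repeat simulations (3,000 to 6,000 runs) gave from-randomisation crossings of 3.1 to 3.6%, 4.0 to 4.3%, 5.9 to 6.8% and 8.2 to 9.9%.

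**4. Failures confined to NCR patients.** With 60% NCR and 12-month PFS of .50 (NCR) and .65 (CR), removing early failures leaves a slightly better mix in the arm that lost more. The from-transplant z moves only 0.01 to 0.08 toward that arm.

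**5. Planned benefit after transplant (.71 v .56).** With 2% failing before day 0 on FluBu and 4% on FluCloBu, the test favours FluCloBu in 90% of runs from transplant and 82% from randomisation. At 2% v 6%, testing once at 156 events against the final boundary, the figures are 90% and 74%.

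**6. Cost of counting failures unrelated to arm.** Simulated power falls from .90 to about .89, .88 and .84 at failure rates of 1%, 2% and 5%. If f early failures carry no treatment effect and D later events do, restoring the planned information needs D/√(D + f) = √156.46.

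- At 2%, f = 250 × .02 = 5, D = 161.3, total about 166 events.
- At 5%, f = 250 × .05 = 12.5, D = 168.1, total about 181 events.

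**The case against.** The strongest reply is that the primary objective concerns patients who receive an allogeneic transplant, so timing from transplant matches the question. The window is short, the only scale in the documents suggests about one failure per arm, and nothing in them points to a difference between arms. The largest effects above need 7% failure in one arm, more than seven times that scale. The from-transplant test keeps its nominal error in the null scenarios with a common hazard. Early deaths could still appear in the toxicity reporting or before the data safety monitoring board. Moving the clock also costs power.

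Much of this stands. The effect may be small, and the finding is not one of false-positive inflation. The toxicity and monitoring provisions mean that early deaths need not be invisible, but they do not bring those deaths into the primary comparison. The appeal to the objective does not settle the matter: reaching transplant comes after randomisation and after the assigned drugs, and a plan that wants a post-transplant question must still say how the other randomised patients are handled.

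The window may also exceed six days. The busulfan test dose can precede admission by up to 10 days and randomisation is not dated. Any time before day -6 could add withdrawals or cancellations, but not toxicity from the drugs that differ.

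**Conclusion.** The concern holds and should be fixed. The documents establish both parts: the primary clock starts three days after the last differing dose, and nothing says how randomised but untransplanted patients enter the analysis. Confidence in this is high.

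The size of the effect is not established. If early failures are equal between arms, the from-transplant test is not shifted. If they differ by a few percentage points, a comparison of all randomised patients would show it and the planned one would not. The figures rest on assumed failure rates, exponential times, 1:1 allocation and the planned accrual rate.

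**What to change.** - Define PFS as time from randomisation to progression or death from any cause, and OS as time from randomisation to death.
- Analyse every randomised patient in the assigned arm, transplanted or not, with CR/NCR status as recorded at randomisation.
- Count progression or death before day 0 as a PFS event. State that a cancelled transplant alone is not an event and that follow-up continues.
- Keep from-transplant PFS as a sensitivity analysis, and report by arm the number randomised but not transplanted, with reasons.

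This is more than a change of wording. If early failures are unrelated to arm, the sponsor must either accept the power loss in step 6 or plan for about 166 events (at 2%) or 181 (at 5%) in place of 156.46, with longer follow-up. The null value of .56 is "based on experience with Flu + IV Busulfan"; the sponsor should check whether that experience was measured from transplant. Each transplanted patient's PFS time lengthens by at least six days. No dose or treatment rule changes.
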